6.2 Secondary analysis

The secondary analysis will be based on the Full Analysis Set and the Safety Analysis Set.

6.2.1 Summary statistics

Secondary endpoints will be summarized with descriptive statistics. Continuous variables will be summarized with n, NA, mean, standard deviation, median and range. Frequency counts and percentage of subjects within each category will be provided for categorical data.

First secondary objective:

Safety analyses will be based on the Safety Analysis Set. All safety analyses will be summarized separately by cohort.

Adverse events will be classified into standardized medical terminology from the verbatim description (investigator term) using the Medical Dictionary for Regulatory Activities (MedDRA). Adverse events will be presented by preferred term (PT) and by system organ class (SOC).

Echocardiogram results (LVEF), and their changes from baseline will be summarized using descriptive statistics. Prolongation of QTc will be analysed using descriptive statistics and frequency tables.

The degree of exposure (dose, duration of treatment, interruptions/reductions of dose) will be assessed to determine the degree to which study safety can be assessed. These results will be presented with descriptive statistics (n, NA, mean, standard deviation, median and range).

Second secondary objective:

The ETS and DpR will be calculated for each cohort. Both ratios will be calculated using the total sum of diameters provided in tumor assessments by central radiology review.

Third secondary objective:

PFS will be calculated using start date of study drug and progression disease or death date (whichever occurs first), based on the Full Analysis set and Per-protocol Analysis Set. PFS censoring rules will follow FDA guidance in 2007 (see Table A).

OS will be calculated using start date of study (C1D1).

A Kaplan Meier survival analysis will be carried out to analyse PFS, providing the median and the corresponding 95% CI of time to progression. Survival curves will be reported.

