#### 20.7 Data Analyses Plans

Summary tables (descriptive statistics and/or frequency tables) will be provided for all baseline variables, efficacy variables, and safety variables, as appropriate. Continuous variables will be summarized with descriptive statistics (n, NA, mean, standard deviation, median and minimum and maximum values). Ninety-five (95) percent confidence intervals may also be presented, as appropriate. Frequency counts and percentage of subjects within each category will be provided for categorical data.

Missing data will be ignored.

Secondary endpoints will be summarized with descriptive statistics. Continuous variables will be summarized with n, NA, mean, standard deviation, median and range. Frequency counts and percentage of subjects within each category will be provided for categorical data. Multivariate regression models may be used to study relations between explanatory variables and primary endpoint. Survival analysis will be performed to analyze PFS, Kaplan & Meyer curves will be presented and possible comparisons will be tested using the log-rank test or the Cox proportional hazard model for multivariate analysis.

Patients with lost of follow-up or treatment discontinuation will be included in the final analysis of primary endpoint if they have at least one tumor assessment and considered as censored data for survival endpoints.

Page 77 of 88 Date: April 04th, 2016

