#### 20.8 Safety Analyses

Safety analyses will be based on the Safety Analysis Set. All safety analyses will be summarized separately by cohort. Adverse events and serious adverse events, laboratory test results, physical examination findings, vital signs, and echocardiogram results (including LVEF), and their changes from baseline will be summarized using descriptive statistics. Abnormal values will be flagged.

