## 20.10 Adverse events

Adverse events will be graded using CTCAE v4.3. Investigators will collect all adverse event CTCAE grades (for both increasing and decreasing severity). Adverse events will be classified into standardized medical terminology from the verbatim description (investigator term) using the Medical Dictionary for Regulatory Activities (MedDRA). Adverse events will be presented by preferred term (PT) nested within system organ class (SOC). Verbatim descriptions and MedDRA SOC and PT for all adverse events will be contained in the data listings of the clinical study report for this protocol.

An overview table, including the incidence of and the number of subjects with TEAEs, SAEs, deaths, and those TEAEs that led to study drug discontinuation, dose modification, or dose interruption will be provided. The incidence of TEAEs will be summarized by SOC, PT, CTCAE grade, and relatedness to study drug. All summaries will be performed by cohort. Although a MedDRA term may be reported more than once for a subject, that subject will be counted only one time in the incidence count for that MedDRA term with the highest CTCAE grade (in the summary by CTCAE grade) or with the closest relationship to study treatment (in the summary by relatedness to study treatment). TEAEs will be defined as adverse events that emerge during treatment, having been absent pretreatment (at baseline) or those that:

- Reemerge during treatment, having been present at baseline but stopped prior to treatment, or
- Worsen in severity during treatment relative to the pretreatment state, when the adverse event is continuous.

Separate summary tables will be provided for: all TEAEs, treatment-emergent SAEs, TEAEs reported as treatment-related, treatment-emergent SAEs reported as treatment-related, and TEAEs leading to treatment discontinuation.

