#### 20.14 Echocardiograms

Echocardiograms (including LVEFs) will be assessed. Summary statistics (mean plus/minus standard deviation, median, and range) for echocardiograms and their changes from baseline will be calculated and summarized for each treatment arm.

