4.2 Secondary objective(s) and secondary variables

The secondary objectives are:

- To determine the safety and tolerability of lenvatinib.
- To estimate the early tumor shrinkage rate and the deepness of response of lenvatinib in each cohort of patients.
- To estimate progression-free survival in both cohorts of patients.

Secondary variables:

- To determine the safety and tolerability of lenvatinib. Safety will be assessed by adverse events (AEs) and serious adverse events (SAEs). Echocardiogram results (LVEF reductions) and QTc (using the QTcB and QTcF values) prolongations will be examined. QTc prolongation will be examined through the adverse events.
- To estimate the early tumor shrinkage (ETS) rate and the deepness of response
 (DpR) of lenvatinib in each cohort of patients:
 - ETS rate is defined as 20% reduction in target lesions after the first 6 weeks of treatment (first tumor assessment).
 - DpR is defined as percentage of maximum tumor shrinkage observed at the nadir (minimum value of total sum of diameters) compared with baseline.

To assess ETS and DpR, total sum of diameters obtained in all tumor assessments will be considered.

• To estimate progression-free survival (PFS) in both cohorts of patients. PFS is defined as the time from the date of treatment start (C1D1) to the date of first documentation of disease progression or death (whichever occurs first) using RECIST 1.1.

Page 9 of 16 Date: June 04, 2020

To evaluate PFS, it will be considered:

- Start date of study drug
- o Progression disease date or death date (whichever comes first)

PFS censoring rules will follow FDA guidance in 2007 [1]:

Table A. PFS 1 (includes documented progression only)

Situation	Date of Progression or Censoring	Outcome
No baseline tumor assessments	Randomization	Censored
Progression documented between scheduled	Earliest of:	Progressed
visits	 Date of radiological assessment showing new lesion (if progression is based on new lesion); or Date of last radiological assessment of measured lesions (if progression is based on 	
	increase in sum of measured lesions)	6 1
No progression	Date of last radiological assessment of measured lesions	Censored
Treatment discontinuation for undocumented progression	Date of last radiological assessment of measured lesions	Censored
Treatment discontinuation for toxicity or other reason	Date of last radiological assessment of measured lesions	Censored

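### The SAP says LVEF reductions will be examined, but the LVEF-specific analyses are continuous summaries that do not show how many patients had a fall

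*SAP*

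**What the plan says.** SAP 4.2 sets out the cardiac part of the safety objective: "Echocardiogram results (LVEF reductions) and QTc (using the QTcB and QTcF values) prolongations will be examined". The following sentence there adds that QTc prolongation will be looked at by way of adverse events.

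SAP 6.2.1 gives the LVEF analysis: "Echocardiogram results (LVEF), and their changes from baseline will be summarized using descriptive statistics". By that section's rule for continuous variables, this means n, number not available, mean, SD, median and range. Protocol 20.14 agrees; it plans "Summary statistics (mean plus/minus standard deviation, median, and range) for echocardiograms and their changes from baseline". For QTc, the next sentence of SAP 6.2.1 reads: "Prolongation of QTc will be analysed using descriptive statistics and frequency tables".

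Echocardiograms are due at screening and every 24 weeks on treatment, or sooner if clinically indicated (protocol Table 4). The LVEF value is entered on the eCRF (protocol 13.8). The only LVEF limit in either document is the 50% eligibility threshold in exclusion criterion 10.

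**The concern.** A reduction in LVEF is something that happens to a patient. The useful safety result is how many patients had a fall, and how large it was. The plan names the reduction as its variable and then analyses the average. Gains in some patients can offset falls in others, and the range shows only the single largest fall. Neither document says what counts as a reduction or plans a count from the echocardiogram values. By contrast, SAP 6.3 defines a tumor-marker reduction (50% or more from baseline) and tabulates it.

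At stake is whether the report can state how many patients lost ventricular function while taking lenvatinib. No efficacy result depends on it.

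**Working it through.** The documents give no figure for LVEF falls, so there is none to reproduce. The check has two steps.

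**Step 1. Does any other provision fix a count?**

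- SAP 6.2.1, general rule: "Frequency counts and percentage of subjects within each category will be provided for categorical data". This needs a category, and none is defined for LVEF.
- Protocol 20.7: "Summary tables (descriptive statistics and/or frequency tables) will be provided for all baseline variables, efficacy variables, and safety variables, as appropriate". This permits a frequency table for LVEF but does not specify one.
- Protocol 20.8, which covers LVEF: "Abnormal values will be flagged". It states no LVEF limit and no count.
- Protocol 20.10: "The incidence of TEAEs will be summarized by SOC, PT, CTCAE grade, and relatedness to study drug". This does count falls, by preferred term and grade, once they are reported as adverse events. Protocol section 14 gives explicit reporting triggers for laboratory values and for ECGs, and none that names echocardiograms. Its clause on deteriorating clinical tests is limited to measurements that the protocol does not require, whereas the echocardiogram is required. Reporting a symptom-free fall therefore rests largely on the investigator's judgement.

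None of these yields a systematic per-patient count from the echocardiogram values.

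**Step 2. Do the planned statistics determine the count?**

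Assumptions, not taken from the documents: 40 of a cohort's 55 patients have a post-baseline echocardiogram, each has one, and every baseline is 60%. Changes are in LVEF percentage points.

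| Change | Case X, patients | Case Y, patients |
|---|---|---|
| -20 | 1 | 1 |
| -12 | 0 | 2 |
| 0 | 32 | 20 |
| +6 | 0 | 16 |
| +12 | 7 | 1 |
| Total | 40 | 40 |

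- Sum, X: -20 + 7 × 12 = 64. Sum, Y: -20 - 24 + 96 + 12 = 64.
- Sum of squares, X: 400 + 7 × 144 = 1408. Sum of squares, Y: 400 + 288 + 576 + 144 = 1408.
- Mean, both: 64/40 = +1.60.
- SD, both: √[(1408 - 40 × 1.60²)/39] = √(1305.6/39) = 5.79.
- Median, both: 0. The 20th and 21st ordered values are zero in X (1 negative, 32 zero, 7 positive) and in Y (3 negative, 20 zero, 17 positive).
- Range, both: -20 to +12.

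The planned output is identical, but the patient counts differ:

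| Patients with | Case X | Case Y |
|---|---|---|
| Any fall | 1 (2.5%) | 3 (7.5%) |
| Fall of at least 5 points | 1 | 3 |
| Fall of at least 10 points | 1 | 3 |
| Fall of at least 15 points | 1 | 1 |
| Fall of at least 20 points | 1 | 1 |
| Lowest LVEF below 50%, baseline 60% | 1 | 3 |
| Lowest LVEF below 50%, baseline 72% | 0 | 0 |

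The contrast holds for every cutoff from any fall up to 12 points. The last row shows why a 50% level cannot serve alone: from a 72% baseline, a 20-point fall ends at 52% and is missed.

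The assumed 40 is not critical. Adding or removing patients with zero change equally in both cases keeps the two outputs identical to each other. With 55 assessed, both have mean 64/55 = 1.16 and SD √[(1408 - 64²/55)/54] = 4.97. With 36 assessed, both have mean 64/36 = 1.78 and SD √[(1408 - 64²/36)/35] = 6.08. Median, range and counts (1 against 3) do not change anywhere between 36 and 55.

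**The case against.** SAP 4.2 promises only that reductions will be examined, not that they will be counted, so it does not contradict SAP 6.2.1. The range always shows the largest fall, so a severe one cannot be hidden. The adverse event definition is broad, and reported events are counted per patient. The example was built so that the two cases match, and it differs by only two patients; exact 95% intervals for 1/40 (0.06% to 13.16%) and 3/40 (1.57% to 20.39%) overlap widely. LVEF is on the eCRF, so a table could be produced at any time.

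Much of this stands. It limits the gap to falls seen on echocardiogram but not reported as adverse events, and it makes the weight minor. It does not remove the point: a summary of averages does not describe how many patients fell, and a cutoff chosen after the data are seen is worth less than one fixed beforehand. The overlapping intervals do not bear on it, because the issue is what the output can show, not whether X and Y differ statistically.

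A reader might infer from SAP 6.2.1 that LVEF was singled out for weaker treatment than QTc. The documents do not support that. The SAP sets no QTc cutoff either, and SAP 4.2 also sends QTc prolongation through adverse events, so the contrast concerns the type of table only. What does differ is that protocol sections 14 and 20.13 give QTc an adverse event trigger (an increase of 60 msec or more), while no trigger names echocardiograms.

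**Conclusion.** The point holds as a cheap improvement of minor weight. The plan names LVEF reductions as a safety variable, and its LVEF-specific analyses cannot show how many patients had one. This follows from the text and needs no assumption. The numerical example rests on the stated assumptions about patients assessed, baseline and pattern of change, and shows possibility, not likelihood.

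It would go too far to infer that LVEF falls will go uncounted altogether: those reported as adverse events will be tabulated. The point concerns one safety parameter in an exploratory phase II study. No data are lost, and neither the primary endpoint nor the sample size is affected.

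**What to change.** In SAP 6.2.1, add one frequency table by cohort among patients with a baseline and at least one post-baseline echocardiogram, scheduled or unscheduled:

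1. n (%) by worst on-treatment absolute fall from baseline, in fixed cumulative categories, for example any fall and falls of at least 5, 10, 15 and 20 points.
2. n (%) whose lowest on-treatment LVEF is below 50%. This is the trial's own eligibility limit, used as a level and not as the definition of a reduction.

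The categories need to be fixed in the text. If worst change were summarised only by mean, SD, median and range, cases X and Y would still look the same. Also report how many treated patients have no post-baseline echocardiogram, and keep the continuous summary. Exact confidence intervals are optional.

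The cost is one extra descriptive table from values already collected, with no new procedure. It cannot repair sparse measurement: the first scheduled on-treatment echocardiogram falls at about week 24, and the off-treatment list in protocol 13.3.1 includes an ECG but no echocardiogram. Patients who stop earlier without an unscheduled one remain unassessed; the table gives their number but cannot fill the gap.

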6.2.2 Statistical inference

Comparisons using log rank test or model of Cox proportional hazards multivariate analysis will be used if needed.

6.3 Exploratory analysis

First secondary objective:

Significant reductions of tumor markers (CgA, 5-HIAA and NSE), defined as reductions of 50% or more regard the baseline values, will be showed by frequency tables.

To examine the relationship of biochemical response with PFS and radiological response the Kaplan-Meier and Chi-square/Fisher methods will be used.

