#### 5.3.3 Exploratory objectives

- To evaluate biochemical response (changes in CgA and NSE levels) and its association with response rate and progression-free survival.
- To assess whether baseline tumor and blood biomarkers may be predictive of response to lenvatinib.
- To explore additional hypotheses related to biomarkers and relationship to lenvatinib, neuroendocrine tumors, other endocrine disorders and/or cancer which may arise from internal or external research activities.

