**Table 5 Clinical laboratory tests** 

Category	Tests
Hematology	
 
Hematocrit, hemoglobin, RBC, platelet count, WBC with differential (bands, basophils, eosinophils, lymphocytes, monocytes, neutrophils), MCH, MCHC, MCV
 
INRa
 

Clinical Chemistry	
Screening visit	
 
Pregnancy test (serum or urine β-hCG)b
 
Bicarbonate, chloride, potassium, sodium, BUN or urea, creatinine, glucose, magnesium, phosphorus, calcium, albumin, total protein, alkaline phosphatase, ALT, AST, conjugated (direct) bilirubin, total bilirubin
 
TSH
 
Chromagranin A (pancreatic origin patients)
 
Chromagranin A +5 HIAA (only for gastrointestinal origin patients)
 
Levels of NSEe
 

Treatment visits without tumor assessment	Bicarbonate, chloride, potassium, sodium, BUN or urea, creatinine, glucose, magnesium, phosphorus, calcium, albumin, total protein, alkaline phosphatase, ALT, AST, conjugated (direct) bilirubin, total bilirubin
Treatment visits with tumor assessment	
 
Bicarbonate, chloride, potassium, sodium, BUN or urea, creatinine, glucose, magnesium, phosphorus, calcium, albumin, total protein, alkaline phosphatase, ALT, AST, conjugated (direct) bilirubin, total bilirubin
 
TSH
 
Chromagranin A (pancreatic origin patients)
 
Chromagranin A +5 HIAA (only for gastrointestinal origin patients)
 
Levels of NSEe
 

Urine analysis c	glucose, hemoglobin (or blood), ketones, pH, protein specific gravity d

ALT = alanine aminotransferase; AST = aspartate aminotransferase;  $\beta$ -hCG = beta human chronionic gonadotropin; BUN = Blood urea nitrogen; CPK=creatine phosphokinase; INR=International Normalized Ratio; LDH= lactate deshidrogenase; MCH=mean corpuscular hemoglobin; MCHC= mean corpuscular hemoglobin concentration; MCV=mean corpuscular volume; NSE = neuron-specific enolase; RBC=red blood cells; T4=thyroxine; TSH=thyroid stimulating hormone; WBC=White blood cells

- a) INR should only be performed as part of the screening (baseline) assessment and when clinically indicated.
- b) Pregnancy test should be performed during 72 hours prior to the study drug administration.
- c) If urinanalysis suggests a urinary tract infection, or if clinically indicated, a urine microscopy, culture and sensitivity should be performed at the EudraCT no.: 2015-001467-39

Page 57 of 88 Date: April 04th, 2016

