#### 20.11 Laboratory values

Clinical laboratory values will be evaluated for each laboratory parameter by subject. Abnormal laboratory values will be identified as those outside (above or below) the normal range. Reference (normal) ranges for laboratory parameters will be included in the clinical study report for this protocol. Descriptive summary statistics for laboratory parameters and their changes from baseline will be calculated. Laboratory parameters that are graded in CTCAE v4.03 will be summarized by CTCAE grade.

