4.3 Exploratory objective(s) and variables

The exploratory objectives are:

- To evaluate biochemical response (changes in CgA, 5-HIAA and NSE levels) and its association with response rate and progression-free survival.
- To assess whether baseline tumor and blood biomarkers may be predictive of response to lenvatinib.
- To explore additional hypotheses related to biomarkers and relationship to lenvatinib, neuroendocrine tumors, other endocrine disorders and/or cancer which may arise from internal or external research activities.

Exploratory variables:

- The changes in tumor markers (CgA, 5-HIIAA and NSE) will be analysed by cohort and significant reductions defined as 50% reduction or more regarding the baseline values will be calculated.
- The relationship between reductions and PFS and radiological response will be assessed.

EudraCT number: 2015-001467-39

Confidential Version 2.0

Page 10 of 16 Date: June 04, 2020

The second and third exploratory objectives will be assessed in the final analysis not in the interim analysis. According to the biomarkers that are available, the analysis of these objectives will be specified.

5. Study populations

The analysis sets will be defined as follows:

- Full Analysis Set will include all allocated subjects. This will be primary analysis set for the efficacy endpoints.
- Per Protocol Analysis Set will include those subjects who were allocated and received at least one dose of the assigned study drug and had no major protocol deviations. The subjects will complete both baseline and at least one post-baseline tumor assessments (week 6). Experior will send a list of major protocol deviations to establish the per-protocol set after the close out of data base. The PI ([name]) will decide which patients should be excluded to define the per protocol analysis set.
- Safety Analysis Set will include all subjects who were allocated and received at least one dose of the study drug and had at least one post-baseline safety evaluation (week 6). This will be the analysis set for all safety evaluations.

6. Statistical strategy

Below are detailed the statistical aspects of the data analysis.

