6.11 Handling of missing data

No planned procedure of imputation of missing values. The analysis will be performed with the available data.

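### Biochemical response has no raised-baseline condition, so its rate and its link to ORR and PFS are mixed up with baseline marker status

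*SAP*

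**What the plan says.** Protocol 5.3.3 sets the first exploratory objective: "To evaluate biochemical response (changes in CgA and NSE levels) and its association with response rate and progression-free survival". SAP 4.3 adds 5-HIAA to the markers. It says that marker changes will be analysed by cohort and that "significant reductions defined as 50% reduction or more regarding the baseline values will be calculated". SAP 6.3 repeats the 50% rule for frequency tables, with significant reductions "defined as reductions of 50% or more regard the baseline values", and then plans the association: "To examine the relationship of biochemical response with PFS and radiological response the Kaplan-Meier and Chi-square/Fisher methods will be used".

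No other section adds a condition on the baseline value:

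- The eligibility criteria (Protocol 8.1 and 8.2) do not require a raised marker.
- The Full Analysis Set in SAP section 5 "will include all allocated subjects". The Per Protocol and Safety sets carry no marker condition. The Pharmacodynamic set in Protocol 20.2 asks for evaluable data but does not mention a normal limit.
- SAP 6.11 plans no imputation: "The analysis will be performed with the available data".

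CgA is scheduled in both cohorts. 5-HIAA is measured in one only: "Chromagranin A +5 HIAA (only for gastrointestinal origin patients" (Protocol Table 5). NSE is measured only at sites able to run the test (Table 5, note e). Protocol 20.11 plans to identify values outside the normal range and states: "Reference (normal) ranges for laboratory parameters will be included in the clinical study report". The response definition does not use those ranges.

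**The concern.** A marker that is normal at baseline has no tumour-related excess to lose. If it halves, that is mostly assay and biological variation. If it does not halve, that says little about whether the tumour responded. Under the 50% rule as written, such a patient is still classified, usually as a non-responder.

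Two results are affected. The biochemical response rate becomes a blend of response among patients who could show it and noise among those who could not, so it varies with the share of normal baselines. The comparison of ORR and PFS between biochemical responders and non-responders also becomes partly a comparison of raised with normal baselines. A weak or strong association could then be credited to marker response when part of it comes from baseline status.

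**Working it through.** **The plan's own figure.** The documents give no expected biochemical response rate and no share of patients with normal baseline. The only design figure is 55 patients per cohort (Protocol 20.6: 10% against 25% ORR, 5% significance level, 90% power). An exact single-stage calculation reproduces it: declaring success at 10 or more responses in 55 gives one-sided alpha 0.044 and power 0.911. That figure does not depend on the biochemical definition.

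**Assumed inputs, none from the documents.**

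- Share with normal baseline, f: 30% and 60%
- Biochemical response rate in raised-baseline patients: 40%
- Noise halving in normal-baseline patients, h: 0% to 20%
- ORR in raised-baseline biochemical responders: 40%
- ORR in raised-baseline non-responders: 15%
- ORR in normal-baseline patients, q: varied from 5% to 25%

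The two raised-baseline ORRs average 0.4 × 40% + 0.6 × 15% = 25%, the design value in Protocol 20.6.

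**Step 1: the rate.** All-patient rate = (1 − f) × 40% + f × h.

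| f | h = 0% | h = 10% | h = 20% |
|---|---|---|---|
| 30% | 28% | 31% | 34% |
| 60% | 16% | 22% | 28% |

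The rate falls whenever h is below the raised-baseline rate. It would rise if h were above it.

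**Step 2: the association with ORR.** For simplicity take h = 0, so every normal-baseline patient joins the non-responders. The mixed non-responder ORR is [(1 − f) × 0.6 × 15% + f × q] / [(1 − f) × 0.6 + f]. With f = 30% and q = 25% this is (0.063 + 0.075)/0.72 = 19.2%. The difference from 40% is then 20.8 points, against 25 points in raised-baseline patients alone.

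| q | Difference, f = 30% | Difference, f = 60% |
|---|---|---|
| 25% | 20.8 points | 17.9 points |
| 15% | 25.0 points | 25.0 points |
| 10% | 27.1 points | 28.6 points |
| 5% | 29.2 points | 32.1 points |

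The break-even is q = 15%. Above it the contrast shrinks, and below it the contrast grows. PFS is open in the same way, since its direction depends on how normal-baseline patients fare.

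**Step 3: cost of restricting.** Of 55 per cohort, 55 × 0.70 = 38.5 (about 38) remain at 30% normal and 55 × 0.40 = 22 at 60%. The table shows exact power of Fisher's test, two-sided 5%, with q = 25% and h = 0.

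| f | Restricted | All patients |
|---|---|---|
| 30% | 15 v 23 patients: 36% | 15 v 40 patients: 30% |
| 60% | 9 v 13 patients: 17% | 9 v 46 patients: 18% |

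**The case against.** A reader might infer that including normal-baseline patients pulls the association toward no effect. The documents do not support that. It follows only if normal-baseline ORR exceeds the ORR of raised-baseline non-responders. At 10%, the rate that Protocol 20.6 calls unacceptable, the difference grows instead. No section gives ORR or PFS by baseline marker level. A reader might also take 28% or 16% as the expected rate. Those figures need no normal-baseline patient ever to halve, which sits badly with calling such halvings noise.

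Other points on the plan's side stand in part:

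- SAP 6.3 states no denominator, so the inclusion of normal-baseline patients is read from the absence of any exclusion. That is still what following the written rule produces.
- One assumed normal share cannot fit three markers with different availability. The sizes are illustrative.
- SAP 4.3 also plans an analysis of marker changes, and Protocol 20.11 plans to identify values outside the normal range. Raised and normal baselines should therefore be identifiable. This limits the harm but does not alter the response definition.
- Restriction brings little or no power: 36% against 30%, and 17% against 18%. The case for it is a clearer question, not a more sensitive test.
- The objective is exploratory, in a study labelled exploratory.

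**Conclusion.** The point holds as one of confounding by baseline marker status. As defined in SAP 4.3 and 6.3, biochemical response classifies patients who have no excess to lose, and nothing else in the documents removes them. The rate falls if they halve less often than raised-baseline patients. On the assumed inputs, 40% becomes 28-34% with 30% normal and 16-28% with 60% normal. The association with radiological response and PFS is distorted in a direction that the documents do not allow one to determine. The primary endpoint and sample size are untouched, so this is a minor improvement to an exploratory analysis.

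**What to change.** In SAP 4.3 and 6.3, state for each marker separately that the main biochemical response rate, and its association with ORR and PFS, will be analysed in patients whose baseline is above the local upper limit of normal. Report the number with normal baseline, by marker and cohort. Keep the all-patient table as a sensitivity analysis, so that no information is discarded.

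The cost is SAP wording and one extra count. Protocol 13.5 has clinical laboratory tests done at the sites and Protocol 20.11 already plans reference ranges, so no new measurements are needed. The downside is fewer evaluable patients (about 38 of 55 per cohort at 30% normal, 22 at 60%, and fewer for NSE where sites cannot test it), with little or no gain in power.
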